10 STATISTICAL CONSIDERATIONS

10.1 Study Design/Study Endpoints

This is a pilot study of GDC-0449 in steroid refractory chronic GVHD. This is a single-institution study that will be performed at the Huntsman Cancer Institute. Total duration of study will be 2 years.

10.1.1 Primary Endpoint

- FFS at 6 months after initiation of therapy with GDC-0449
FFS is defined as absence of NRM, no recurrent malignancy, steroid dose at 6 months ≤ 0.2 mg/kg/d of PDE, and no addition of new systemic treatment for chronic GVHD (Adapted from [45]). Criteria for addition of new systemic treatment for chronic GVHD are defined as per [section 9.0](#).

10.1.2 Secondary Endpoints

- Safety of GDC-0449 in patients with steroid-refractory chronic GVHD
- Change in NIH global score of chronic GVHD from baseline at 6 and 12 months after the initiation of the protocol therapy
 - NIH global score will be defined by using the NIH consensus criteria for assessment of chronic GVHD severity [46].
- One-year NRM and one-year relapse rate
 - Relapse will be defined as malignancy relapse or as the initiation of any unintended intervention including an unplanned taper of immunosuppressant therapy to prevent malignancy progression due to any signs of recurrent, residual or new malignant disease after transplantation.
- One-year FFS and one-year OS
 - FFS is defined as in section 10.1.1 (Primary Endpoint).
- Clinical characteristics that may be associated with decreased FFS including the presence of high-risk disease at transplantation; high-intensity conditioning with total-body irradiation; > 3 involved sites with chronic GVHD, lower gastrointestinal involvement by GVHD and severe NIH global score at initiation of protocol treatment; and thrombocytopenia, hyperbilirubinemia, and steroid doses >1 mg/kg per day immediately before treatment failure requiring treatment change.
- Clinical response to GDC-0449 at 6 months as defined in section 9.1.2.

10.1.3 Exploratory Endpoints

- Fibrocyte numbers, leukocyte subsets and T cell cytokine profiles will be determined at baseline and in response to GDC-0449 at 3, 6, 9 and 12 months using flow cytometry.
- Cytokine profiles and ECM biomarkers present in plasma will be determined at baseline and in response to GDC-0449 at 3, 6, 9 and 12 months using ELISA and the fibroplex assay
- Mesenchymal cell phenotypes cultured from skin biopsies of cutaneous cGVHD patients pre- and post-GDC-0449 will be determined at baseline and in response to GDC-0449 at 6 months using immunohistochemistry studies and mesenchymal cell cultures
- Levels of TGF β and hedgehog activation will be determined on skin biopsies at baseline and in response to GDC-0449 at 6 months, using different staining and other techniques.

10.2 Sample Size/Accrual Rate/Other Statistical Considerations

Sample size: 12 patients. Accrual rate: 1-2 patients monthly.

This is a pilot study that will include 12 patients. FFS, the primary endpoint, will be evaluated using the Kaplan-Meier method. The impact of different covariates on FFS will be analyzed using descriptive statistics, t-test, and Fisher's exact test where applicable. Differences in NIH scores will be analyzed using Wilcoxon signed-rank test. Differences in biomarkers will be assessed using Wilcoxon rank-sum test.

Overall clinical response (PD, SD, PR, CR) according to NIH criteria will be tabulated and described based on organ response and overall response.

The proportion of subjects who experience adverse events and serious adverse events will be summarized descriptively; no inferential tests will be performed.

10.3 Stratification Factors

N/A

10.4 Analysis of Secondary Endpoints

See [Sections 10.1](#).

11 REGISTRATION GUIDELINES

11.1 Investigator and Research Associate Registration with CTEP

11.1.1 CTEP Registration Procedures

Food and Drug Administration (FDA) regulations and National Cancer Institute (NCI) policy require all investigators participating in any NCI-sponsored clinical trial to register and to renew their registration annually.

Registration requires the submission of:

- a completed **Statement of Investigator Form** (FDA Form 1572) with an original signature
- a current Curriculum Vitae (CV)
- a completed and signed **Supplemental Investigator Data Form** (IDF)
- a completed **Financial Disclosure Form** (FDF) with an original signature

Fillable PDF forms and additional information can be found on the CTEP website at http://ctep.cancer.gov/investigatorResources/investigator_registration.htm.

For questions about Investigator Registration, please contact the **CTEP Investigator Registration Help Desk** by email at [contact]

11.1.2 CTEP Associate Registration Procedures / CTEP-IAM Account

The Cancer Therapy Evaluation Program (CTEP) Identity and Access Management (IAM) application is a web-based application intended for use by both Investigators (i.e., all physicians involved in the conduct of NCI-sponsored clinical trials) and Associates (i.e., all staff involved in the conduct of NCI-sponsored clinical trials).

Associates will use the CTEP-IAM application to register (both initial registration and annual re-registration) with CTEP and to obtain a user account.

Investigators will use the CTEP-IAM application to obtain a user account only. (See CTEP Investigator Registration Procedures above for information on registering with CTEP as an Investigator, which must be completed before a CTEP-IAM account can be requested.)

An active CTEP-IAM user account is required to access all CTEP applications and, if applicable (e.g., all Network trials), all Cancer Trials Support Unit (CTSU) applications and websites.

Additional information can be found on the CTEP website at http://ctep.cancer.gov/branches/pmb/associate_registration.htm.

11.2 Patient Registration:

Patients must meet all of the eligibility requirements listed in Section 4 prior to registration.

Study related screening procedures can only begin once the patient has signed a consent form. Patients must not begin protocol treatment prior to registration.

Treatment should start within 5-7 business days after registration.

To register eligible patients on study, complete a Clinical Trials Office Patient Registration Form and submit to: [contact].

IWRS

Patient Enrollment will be facilitated using the Interactive Web Response System (IWRS). IWRS is a web-based registration system available to users on a 24/7 basis. On a successful registration, IWRS will assign a patient number and assign the treatment. Patient enrollment data entered by Registrars in IWRS will automatically transfer to the NCI's clinical data management system, Medidata Rave. IWRS will provide a printable confirmation of registration and treatment information. Please print this confirmation for your records.

- Users must have a valid CTEP-IAM account (i.e., CTEP username and password) to access the IWRS system.
- Users defined with the Registrar role will have the ability to register patient in the study.
- Users defined with the Client Administrator role will have the ability to manage accrual limits, open and close treatment assignments as well as approve slot reservations, if applicable to the study.
- For trials with slot reservation requirements, Registrars will have the ability to request to reserve a slot, which may require approval from users at the lead institution defined as a 'Client Administrator' for the study.

12 DATA REPORTING / REGULATORY REQUIREMENTS

Adverse event lists, guidelines, and instructions for AE reporting can be found in [Section 14.0](#) (Adverse Events: List and Reporting Requirements).

12.1 Data Reporting

Data collection for this study will be done exclusively through Medidata Rave. Access to the trial in Rave is granted through the iMedidata application to all persons with the appropriate roles assigned in the Regulatory Support System (RSS). To access Rave via iMedidata, the site user must have an active CTEP IAM account (<https://eapps-ctep.nci.nih.gov/iam>) and the appropriate Rave role (Rave CRA, Read-Only, or Site Investigator) on either the Corresponding Organization or Participating Organization roster at the enrolling site.

Upon initial site registration approval for the study in RSS, all persons with Rave roles assigned on the appropriate roster will be sent a study invitation e-mail from iMedidata. To accept the invitation, site users must log into the Select Login (<https://login.imedidata.com/selectlogin>) using their CTEP-IAM user name and password, and click on the "accept" link in the upper right-corner of the iMedidata page. Please note, site users will not be able to access the study in Rave until all required Medidata and study specific trainings are completed. Trainings will be in the form of electronic learnings (eLearnings), and can be accessed by clicking on the link in the upper right pane of the iMedidata screen.

Users that have not previously activated their iMedidata/Rave account at the time of initial site registration approval for the study in RSS will also receive a separate invitation from iMedidata to activate their account. Account activation instructions are located on the CTSU website, Rave tab under the Rave resource materials (Medidata Account Activation and Study Invitation Acceptance). Additional information on iMedidata/Rave is available on the CTSU members' website under the Rave tab or by contacting the CTSU Help Desk at [name] or by e-mail at [contact].

12.1.1 Method

This study will be monitored by the Clinical Trials Monitoring Service (CTMS). Data will be submitted to CTMS at least once every two weeks via Medidata Rave (or other modality if approved by CTEP). Information on CTMS reporting is available at <http://www.theradex.com/CTMS>. On-site audits will be conducted three times annually (one annual site visit and two data audits). For CTMS monitored studies, after users have activated their accounts, please contact the Theradex Help Desk at [contact] or by email at [contact] for additional support with Rave and completion of CRFs.

12.2 CTEP Multicenter Guidelines

N/A

12.3 Collaborative Agreements Language

The agent(s) supplied by CTEP, DCTD, NCI used in this protocol is/are provided to the NCI under a Collaborative Agreement (CRADA, CTA, CSA) between the Pharmaceutical Company(ies) (hereinafter referred to as “Collaborator(s)”) and the NCI Division of Cancer Treatment and Diagnosis. Therefore, the following obligations/guidelines, in addition to the provisions in the “Intellectual Property Option to Collaborator” (http://ctep.cancer.gov/industryCollaborations2/intellectual_property.htm) contained within the terms of award, apply to the use of the Agent(s) in this study:

1. Agent(s) may not be used for any purpose outside the scope of this protocol, nor can Agent(s) be transferred or licensed to any party not participating in the clinical study. Collaborator(s) data for Agent(s) are confidential and proprietary to Collaborator(s) and shall be maintained as such by the investigators. The protocol documents for studies utilizing Agents contain confidential information and should not be shared or distributed without the permission of the NCI. If a copy of this protocol is requested by a patient or patient’s family member participating on the study, the individual should sign a confidentiality agreement. A suitable model agreement can be downloaded from: <http://ctep.cancer.gov>.
2. For a clinical protocol where there is an investigational Agent used in combination with (an)other Agent(s), each the subject of different Collaborative Agreements, the access to and use of data by each Collaborator shall be as follows (data pertaining to such combination use shall hereinafter be referred to as "Multi-Party Data"):
 - a. NCI will provide all Collaborators with prior written notice regarding the existence and nature of any agreements governing their collaboration with NCI, the design of the proposed combination protocol, and the existence of any obligations that would tend to restrict NCI's participation in the proposed combination protocol.
 - b. Each Collaborator shall agree to permit use of the Multi-Party Data from the clinical trial by any other Collaborator solely to the extent necessary to allow said

other Collaborator to develop, obtain regulatory approval or commercialize its own Agent.

- c. Any Collaborator having the right to use the Multi-Party Data from these trials must agree in writing prior to the commencement of the trials that it will use the Multi-Party Data solely for development, regulatory approval, and commercialization of its own Agent.
3. Clinical Trial Data and Results and Raw Data developed under a Collaborative Agreement will be made available to Collaborator(s), the NCI, and the FDA, as appropriate and unless additional disclosure is required by law or court order as described in the IP Option to Collaborator (http://ctep.cancer.gov/industryCollaborations2/intellectual_property.htm). Additionally, all Clinical Data and Results and Raw Data will be collected, used and disclosed consistent with all applicable federal statutes and regulations for the protection of human subjects, including, if applicable, the *Standards for Privacy of Individually Identifiable Health Information* set forth in 45 C.F.R. Part 164.
4. When a Collaborator wishes to initiate a data request, the request should first be sent to the NCI, who will then notify the appropriate investigators (Group Chair for Cooperative Group studies, or PI for other studies) of Collaborator's wish to contact them.
5. Any data provided to Collaborator(s) for Phase 3 studies must be in accordance with the guidelines and policies of the responsible Data Monitoring Committee (DMC), if there is a DMC for this clinical trial.
6. Any manuscripts reporting the results of this clinical trial must be provided to CTEP by the Group office for Cooperative Group studies or by the principal investigator for non-Cooperative Group studies for immediate delivery to Collaborator(s) for advisory review and comment prior to submission for publication. Collaborator(s) will have 30 days from the date of receipt for review. Collaborator shall have the right to request that publication be delayed for up to an additional 30 days in order to ensure that Collaborator's confidential and proprietary data, in addition to Collaborator(s)'s intellectual property rights, are protected. Copies of abstracts must be provided to CTEP for forwarding to Collaborator(s) for courtesy review as soon as possible and preferably at least three (3) days prior to submission, but in any case, prior to presentation at the meeting or publication in the proceedings. Press releases and other media presentations must also be forwarded to CTEP prior to release. Copies of any manuscript, abstract and/or press release/ media presentation should be sent to:

Email: [contact]

The Regulatory Affairs Branch will then distribute them to Collaborator(s). No publication, manuscript or other form of public disclosure shall contain any of Collaborator's confidential/ proprietary information.

13 BIOMARKER, CORRELATIVE, AND SPECIAL STUDIES

13.1 Biomarker Studies

All studies in this section are ancillary/exploratory. The aim of these studies is to determine the impact of GDC-0449 treatment on parameters of ECM turnover and immunologic changes in the circulation, as well as on markers of HH signaling in cGVHD skin biopsies.

13.1.1 Proteomic chronic GVHD analysis in Plasma:

Plasma will be collected for proteomic analysis of chronic GVHD biomarkers and extracellular matrix production and turnover. Analysis will include, but not be limited to, osteopontin, ST2, BAFF, MMP3, TGF- β , and CXCL9.

13.1.2 Immunologic Monitoring in Peripheral Blood:

Immunological monitoring will be performed using peripheral blood mononuclear cells collected prior to the initiation of therapy and then at 3, 6, 9 and 12 months (5 time points per patient)

13.1.2.1 Immune Cell Subsets:

The main objectives of the monitoring will be to characterize changes in immune subsets with well-defined or emerging roles in immunopathology of chronic GVHD (T cells, B cells, and monocytes/dendritic cells) and correlate findings with the clinical outcome. Analyses will utilize multicolor flow cytometry to profile helper and regulatory CD4⁺ T cells, effector CD8⁺ T cells, circulating monocytes, and B cells and define impact of GDC-0449.

Regulatory T cell analyses (CD3⁺ CD4⁺ CD25⁺ Foxp3⁺) will focus on markers of their suppressive potential with likely functional impact in chronic GVHD (such as Helios and CTLA- [53-57]). Th1/Th2/Th17 polarization among helper T cells will be analyzed by flow cytometry, evaluating canonical transcription factors Tbet, GATA3, and ROR γ and cytokine production in re-stimulated T cells. In addition, sort purified CD4⁺ and CD8⁺ T cells will be transcriptionally profiled for broader cytokine production and changes that occur under GDC-0449.

B cells are well documented mediators of chronic GVHD and represent an intermediary step in triggering fibrotic tissue response. We will provide immunophenotypic analyses and focus on characterization of GDC-0449 impact on defined subsets with pathogenic relevance in chronic GVHD, including “autoreactive” CD27^{neg}CD21^{low}, pre-germinal center CD27⁺IgD⁺CD38^{hi}, and plasmablast-like CD27⁺IgD^{low}CD38^{hi} B cells in peripheral blood. In addition, B cells will be sort purified to evaluate transcriptionally impact of GDC-0449 on Hh target genes.

Emerging evidence supports key role for alternative macrophage activation and polarization in fibrotic tissue remodeling in chronic GVHD, and pre-clinical studies have identified early monocyte polarization is essential for fibrotic GVHD onset. We will profile impact of GDC-0449 on subsets of patrolling (CX3CR1^{high}CD14^{dim}CD16⁺) and classical (CCR2^{high}CD14⁺CD16⁻) monocytes by flow cytometry. In addition, we will sort purify bulk monocytes and transcriptionally analyze for regulation of Hh target genes and classically vs

alternative polarization towards macrophages.

The effect of GDC-0449 on immune subsets remains uncharacterized aside for pre-clinical reports of no impact on leukocyte tissue infiltration in models of chronic fibrotic GVHD. Pre-clinical data suggest impact of Hh signaling on innate immunity, thus, if clinical benefit is documented, we hypothesize biggest differences will be seen in the pool of peripheral blood monocytes. While Hh pathway has been shown to play a role in T cell development its impact on mature T cell responses remains undefined. We postulate that Hh will not influence T cell polarization or function, nor B cell responses directly, and possible clinical benefits will be largely derived through its impact on myeloid regulation and/or terminal tissue remodeling functions. Importantly, our studies will document the effects of GDC-0449 on adaptive immunity and thus inform of the possible immunosuppressive effects of this therapy that could pose further risks to patients with chronic GVHD.

Flow Cytometry panels:

Panel 1: Treg	Panel 2: T helper	Panel 3: B cells / Monocytes	Panel 4: Sort
41BB	IL-17	CD3	CD3
CD4	CD4	CCR2	CD4
CD127			
ICOS	IFNg	CD14	CD14
FoxP3	RORc	CD64	CD64
PD-1		CD20	CD20
Helios	GATA3	CD38	
OX40	IL-4	CD16	CD16
		IgD	
CD25	Tbet	CX3CR1	
CD3	CD3		
CTLA-4		CD27	
CD8		CD21	CD8
Viability	Viability	Viability	Viability

13.1.2.2 Platelet Function Assay

Assay description	Proposed candidates
Whole blood flow cytometric assay for platelet activation	CD41, P-selectin, PAC-1, CD154 (CD40L).
Isolated platelets flow cytometric assay for platelet apoptosis and immune functions	Annexin V, Caspase-3, Bcl-2, MHC class I, CXCR4, CCL5 (RANTES), PDGF, PF4(CXCL4), TGF- β , TNF- α .
Ex vivo stimulated platelets flow cytometric assay for platelet activation and immune functions	CD41, P-selectin, PAC-1, CD154 (CD40L), CXCR4, CCL5, PDGF, VEGF, PF4, TGF- β , TNF- α .
ELISA for the quantification of platelet released cytokine and growth factors upon stimulation ex vivo	VEGF, PDGF, TGF- β , TNF- α , IL-1, IL-6, serotonin.
Western immunoblotting of isolated platelet lysates and ex vivo stimulated platelet lysates for the characterization of Wnt/Shh signaling pathway	Wnt, β -Catenin and phospho- β -Catenin.
RNA sequencing of platelets	Global genetic signature characterization of platelets.
Validation at protein level of candidates screened from RNA sequencing data	Dependent on the RNA sequencing data.

Abbreviations:

CCL5: Chemokine ligand 5

CXCR4: C-X-C chemokine receptor type 4

ELISA: Enzyme-linked immunosorbent assay

PDGF: Platelet derived growth factor

PF4: Platelet factor 4

TGF- β : Transforming growth factor-beta

TNF- α : Tumor necrosis factor

VEGF: Vascular endothelial growth factor

Whole blood will be drawn from consenting patients and controls using sterile, ACD-containing, BD vacutainer tubes. We will draw approximately 40mLs of whole blood from each patient or control at each time point. Blood will be used immediately for real-time assays (e.g. whole blood flow cytometry and platelet stimulation assays) and cells and plasma components will also be isolated (e.g. platelets, PBMCs, plasma, plasma-derived microparticles) for studies performed in batches to minimize variability. Table 1 is a proposed list of assays and target candidates. These candidates include canonical indices of platelet activation (e.g. P-selectin, PAC-1), immune and inflammatory molecules expressed by or secreted from platelets (e.g. TNF, CD154, MHC Class I, CCL5), apoptosis markers (e.g. Annexin V), and growth factors (e.g. VEGF). We will also interrogate candidates involved in the hedgehog pathway including Wnt and beta-catenin (both unphosphorylated and phosphorylated forms). Other assays may be included as new targets are identified. Next-generation RNA-sequencing will be done on a subset of patients and controls (n=5-10/group) as a discovery tool to interrogate other genes differentially expressed in patients with GHVD.

13.1.3 Skin Biopsies:

Four mm punch biopsies will be collected at baseline and 6 months from patients enrolled in the study. Biopsies will be cut in half and one half will be fixed and embedded in paraffin for immunohistochemistry studies for the HH stabilized transcription factors GLI-1 and GLI-2. The other half will be used to obtain RNA to test for mRNA expression of SHH, GLI-1, GLI-2,

PTCH 1 and PTCH-2. Samples will be stored in HCI's Biorepository and Molecular Pathology (BMP) storage facility.

Biological parameters will be correlated with clinical markers of disease severity in exploratory longitudinal analyses.

The logistics for obtaining the samples required for the correlative studies are summarized on the Table below:

	Whole Blood	Plasma	Tissue
Collection Timepoints	Baseline, 3, 6, 9, 12 months Collect pre-dose	Baseline, 3, 6, 9, 12 months One time pre-dose	Baseline, 6 months Optional for 1 st patient
Specimen Type/ Amount	(3) Green Top Sodium Heparin 10 ml tubes	(1) Purple Top EDTA 3 ml tube	4 mm Skin Punch Biospy
Processing Instructions	Whole blood will be sent ambient to BMP who will process cells and freeze.	Centrifuge tubes at standard speed and time. Pour off plasma into aliquot tube and freeze.	4 mm bx divided: ½ formalin fixed paraffin embedded, ½ snap frozen in liquid nitrogen.
Storage	BMP until ready to ship	BMP until ready to ship	BMP until ready to ship
Shipping Instructions *e-mail lab prior to shipment to notify of arrival.	Batch ship as directed by the PI	Batch ship as directed by the PI	Batch ship as directed by the PI
Laboratory Location	University of Utah George and Dolores Eccles Institute of Human Genetics [name] [name]	[name] Lab University of Utah Eccles Institute of Human Genetics [name] [name]	

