In all analyses, each patient will serve as their own control by comparing baseline measures with longitudinal results post-treatment. GDC-0449 may have little impact on inflammatory cell numbers in the peripheral blood or IHC specimens based on previous murine results [34]. Whether GDC-0449 will alter T cell cytokine profiles in circulation or in skin is unknown. Patients responding well to this SMO inhibitor may show reduced IL-17 and IFN γ in circulation as these cytokines have been associated with cutaneous manifestations of cGVHD [47]. These same studies showed Th2 cytokines (IL-4/13) were associated with aGVHD. If therapy fails to mediate clinical improvement, it may be due to an inability to inhibit these T cell responses. If GDC-0449 is effective, we anticipate reduced expression of GLI-1, GLI-2, PTCH-1 and PTCH-2 in skin. Because GLI-1 can activate IL-6 and IL-8 [63], these cytokines may be reduced in plasma post-GDC-0449 treatment and this may offer an assay to look for HH activity indirectly. Patients who do not respond may show no reductions in HH signaling (e.g. GLI-1) and this may indicate that drug levels were insufficient. It is also possible that patients may acquire SMO mutations that make them resistant to GDC-0449 [64, 65]. This could be determined by sequence analysis of SMO in those patients. We believe systemic markers of ECM synthesis, turnover and degradation will also be altered by GDC-0449 treatment in patients showing signs of clinical efficacy. We realize that these analyses are exploratory in nature given the relatively small sample size (n=12) for which CTEP agreed to provide study drug. However, these studies are highly significant as they are likely to identify relevant biomarkers that correlate with clinical efficacy or that may explain therapeutic futility. These will be critical insights into designing larger future trials.

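### The platelet assay text asks for fresh ACD blood, but the sample logistics table draws only heparin and EDTA tubes and freezes the cells; the source of the controls is also not stated

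*Combined protocol and SAP*

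**What the plan says.** Two adjacent parts of Section 13.1 give collection instructions.

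- **Platelet text (13.1.2.2).** The tube is specified: "Whole blood will be drawn from consenting patients and controls using sterile, ACD-containing, BD vacutainer tubes". So is the volume: "We will draw approximately 40mLs of whole blood from each patient or control at each time point". On handling: "Blood will be used immediately for real-time assays (e.g. whole blood flow cytometry and platelet stimulation assays". Platelets, mononuclear cells, plasma and microparticles are also to be isolated "for studies performed in batches to minimize variability".
- **Logistics table (after 13.1.3).** It is introduced as summarising how the samples for the correlative studies are obtained. Whole blood is listed as "3) Green Top Sodium Heparin 10 ml tubes", and plasma as a single 3 mL EDTA tube. On processing: "Whole blood will be sent ambient to BMP who will process cells and freeze". Shipping is in batches as the investigator directs. Collection is at baseline and at 3, 6, 9 and 12 months.

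Footnote 6 of the study calendar (Section 7) gives the same five time points and refers the reader to the table in Section 13.1 for details.

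On the comparison to be made, 13.1.2.2 says: "Next-generation RNA-sequencing will be done on a subset of patients and controls (n=5-10/group"), as a discovery tool for genes expressed differently in patients with GVHD. The closing discussion of Section 13.1 says: "In all analyses, each patient will serve as their own control by comparing baseline measures with longitudinal results post-treatment".

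**The concern.** The text and the table cannot both be the complete instruction. The text needs a specific anticoagulant and immediate use. The table provides neither, and the calendar points staff to the table. If staff collect by the table, the real-time assays have no sample. A baseline platelet measurement is lost for good once the patient has been dosed, and with it any before-and-after comparison for that patient.

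The second difficulty is the comparison group. The text refers to controls, but the enrolment and eligibility sections describe only patients with chronic GVHD, and the closing discussion describes a within-patient comparison. The choice decides what is estimated. Patient versus control describes the disease, whereas baseline versus on-treatment addresses the stated aim of Section 13.1, the effect of GDC-0449.

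**Working it through.** **Inputs.** ACD draw: about 40 mL per person per time point (13.1.2.2). Table: 3 tubes of 10 mL heparin and 1 tube of 3 mL EDTA. Time points: 5 (table, calendar footnote 6, 13.1.2). Enrolment: 12 patients (3.2, 10.2). The first 4 subjects had already been assessed for safety after one cycle (9.3).

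**Step 1. Can the stated 40 mL be reproduced from the table?**

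- Whole-blood tubes: 3 × 10 = 30 mL, short by 40 − 30 = 10 mL (10/40 = 25%).
- All blood tubes: 30 + 3 = 33 mL, short by 40 − 33 = 7 mL (7/40 = 17.5%).
- ACD blood in the table: 0 mL.

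The figure is not reproduced either way. The tube type matters more than the shortfall in volume.

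**Step 2. Volume under each reading.**

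| Reading | Per visit | Five time points |
|---|---|---|
| Table only | 33 mL | 33 × 5 = 165 mL |
| ACD draw replaces the table's tubes | 40 mL | 40 × 5 = 200 mL |
| ACD draw is added to them | 40 + 33 = 73 mL | 73 × 5 = 365 mL |

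The five-visit totals assume that the platelet draw follows the table's schedule. 13.1.2.2 does not list its own time points. The totals are maxima, because patients who need added systemic treatment leave the study (9.1).

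**Step 3. Which of the seven listed platelet assays are affected?**

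- Three depend explicitly on fresh whole blood or on ex vivo stimulation: whole-blood activation flow cytometry, flow cytometry of stimulated platelets, and the ELISA for factors released on stimulation.
- The Western blots depend on stimulation in part, since they cover stimulated as well as unstimulated platelet lysates.
- The other three are flow cytometry of isolated platelets, RNA sequencing, and protein validation of the sequencing results. The text allows batched work on isolated components, so freezing alone does not rule these out. The table does not, however, name a platelet isolation step.

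**Step 4. Comparison group.** The planned accrual table (4.3) sums to 2 + 2 + 8 = 12, which is the patient target. It therefore accounts for none of the 5 to 10 controls. If the comparison is instead baseline versus on-treatment, the ceiling is 12 pairs. If the first 4 subjects have no baseline platelet sample, which the documents do not settle, the ceiling is 12 − 4 = 8.

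**The case against.** The strongest reply is that 13.1.2.2 itself orders the ACD tubes, the volume and the immediate use. Section 8.1 also sends staff to Section 13 as a whole, so someone who reads all of it will find the instruction. Samples are lost only if the table is followed alone. This stands, and it limits the point to an unreconciled contradiction. A reader might infer that the sub-study's read-outs cannot be obtained at all. The documents do not support that, because the text orders the right sample and part of the work is batched. What remains is that a careful reader would hold two conflicting instructions and no combined volume.

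On the controls, a reader might infer that there are none. That goes too far. The available copy lacks the consent pages and some text just before the own-control sentence. Controls could also come from outside the 12 treatment places. It can be said only that the available text does not state their source. The material that follows the own-control sentence does not discuss platelets, so its reach over the platelet work is open to argument. It nevertheless says that it covers all analyses.

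A reader might also infer that the patient-versus-control contrast is a mistake. The text gives it a purpose, discovery in GVHD, and it is legitimate for that purpose. It does not measure drug effect.

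Finally, Section 13.1 labels all of this work ancillary and exploratory, and the platelet assays are a proposed list. This stands and sets the severity.

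**Conclusion.** The contradiction is real and visible in the protocol: about 40 mL of ACD blood, partly for immediate use, against 33 mL of heparin and EDTA blood with the whole blood frozen. Following the table alone forgoes at least three of seven platelet assays, and the missed baselines are permanent. That loss is conditional on how staff work. The documents do not show that it has happened.

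The comparison for platelet RNA sequencing is also unreconciled: two groups of 5 to 10 in one place, each patient as their own control in another.

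The impact is minor. Platelet function is not among the exploratory endpoints in 10.1.3, and failure-free survival is unaffected. The correction is still worth making because it is specific and cheap, and it protects samples that cannot be drawn again.

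**What to change.** 1. Add a column for the platelet draw to the Section 13.1 logistics table: ACD tubes, volume, time points, and same-day unfrozen transfer to the platelet laboratory. State whether it replaces the heparin and EDTA tubes (about 40 mL per visit) or adds to them (about 73 mL), and give the combined volume. Name the platelet isolation step for the batched assays. The alternative is to delete the real-time and stimulation assays from 13.1.2.2.
2. For RNA sequencing, either state the source and number of controls and exempt this analysis from the own-control statement, or use baseline versus on-treatment pairs in patients who have a baseline platelet sample, and report how many there are, since this may be fewer than 12.
3. Match the test to that choice. Section 10.2 names the Wilcoxon rank-sum test for biomarkers, which suits two independent groups and not pairs.

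The cost is a table and wording amendment, plus same-day handling of one tube set that the text already plans. Choosing the paired comparison would give up the GVHD-versus-control description.
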